8.4.5 Pharmacodynamic Analyses

Although the final decision on the further evaluation of BMS-663068 will be a broader scientific assessment of its benefit/risk profile, including consideration of safety and other endpoints as previously outlined, plus relevant information external to this trial, a mean decrease from baseline in HIV RNA of at least 1 log₁₀ on Day 9 within any one regimen group may suggest that that dose of BMS-663068 is sufficiently active against HIV.

The magnitude of the change in log₁₀ HIV RNA levels will be assessed by summarizing changes from baseline, including 90% confidence intervals, at study day 2 through day 11 and at day 15, by regimen group and antiretroviral treatment history (ARV naive, ARV experienced, and combined [ARV naive + ARV experienced]). The primary assessment of the antiviral activity of BMS-663068 will be based on the log₁₀ change from baseline in HIV RNA to Day 9. To assess the dependency on dose, scatter plots of log₁₀ change from baseline in HIV RNA at Day 9 versus dose will be provided. Two groups t-test will be used to test the differences in mean log₁₀ decrease in HIV RNA at Day 9 between two regimen groups by antiretroviral treatment history (ARV naive, ARV experienced, and combined [ARV naive + ARV experienced]). Each individual's maximum log₁₀ decrease from baseline in HIV RNA will be summarized by regimen group, antiretroviral treatment history (ARV naive, ARV experienced, and combined [ARV naive + ARV experienced]), and frequency distributions for maximum log₁₀ decrease from baseline in HIV RNA will be provided by regimen group, antiretroviral

treatment history (ARV naive, ARV experienced, and combined [ARV naive + ARV experienced]).

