1.4 Study Rationale

This study is being conducted to assess the antiviral activity, safety, tolerability and PK of selected regimens of BMS-663068 with and without RTV in HIV-1 infected subjects. BMS-663068 is a methyl phosphate prodrug of BMS-626529,^{3,4} and represents one of a

novel class of antiretroviral agents that blocks the first step of viral entry, namely the attachment of viral gp120 envelope to the cellular CD4 receptor. Proof of concept was achieved with a prior HIV attachment inhibitor, BMS-488043, in Protocol AI430003.¹⁴ BMS-488043 at doses of 800 and 1800 mg produced viral load decline of greater than 0.7 log₁₀ copies/mL from baseline on Day 8, thereby providing confidence that the compound has antiviral activity in HIV infected subjects. BMS-488043 was safe and well tolerated; however, a high fat meal were required to achieve adequate exposure. Therefore, development of BMS-488043 was halted. The current formulation of BMS-663068 has improved PK properties and BMS-626529 has an ~ 16 fold slower off rate; thus, BMS-663068 should produce antiviral effects at least as good as BMS-448043 without the undesirable dosing requirements.

BMS-626529, the active moiety of BMS-663068, is efficacious against macrophage-, T-cell-, and dual tropic laboratory HIV-1 strains. Given the in vitro sensitivity of BMS-626529, it is anticipated that BMS-663068 will be most effective at inhibiting entry of clade B HIV-1; therefore, this study will restrict enrollment to subjects infected by HIV-1 clade B. Clade B HIV is a frequent encountered clade in many parts of the world, including North /Central/South America and Europe.

In study AI430003, antiviral effect of BMS-488043 was greater in treatment naive patients compared to treatment experienced patients. Viral susceptibility and exposure to the study drug, especially C_{min} values, were lower in treatment experienced patients compared to treatment naive patients. This was an unexpected finding without a clear explanation; therefore, the current study will be stratified to assess the antiviral activity of BMS-626529 in antiretroviral naive versus experienced subjects to reassess the prior finding.

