2.3 Exploratory Objectives

- To explore the effect of BMS-626529 following multiple regimens of BMS-663068 with and without RTV on activated (DR+) CD4+ and CD8+ subsets
- To explore the effect of BMS-626529 following multiple regimens of BMS-663068 with and without RTV on neutralizing antibody activity
- To explore the effect of BMS-626529 following multiple regimens of BMS-663068 with and without RTV on HIV co-receptor usage (CCR5 versus CXCR4) and to explore the relationship between HIV co-receptor usage and antiviral activity
- To explore the difference in antiviral activity of BMS-626529 following multiple regimens of BMS-663068 with and without RTV by prior antiretroviral (ARV) treatment history (ARV naive versus ARV experienced)
- To explore the change in viral susceptibility measured by envelope genotype and phenotype

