4 INVESTIGATIONAL PLAN

4.1 Study Design and Duration

This is a randomized, open label, multiple-dose parallel study. Subjects will undergo screening evaluations to determine eligibility within 35 days prior to study enrollment. Subjects will be admitted to the clinical facility the evening prior to dosing (Day -1). Subjects will be randomized into one of 5 regimen groups: Group 1 - BMS-663068 600 mg Q12H + RTV 100 mg Q12H; Group 2 - BMS-663068 1200 mg QHS + RTV 100 mg QHS; Group 3 - BMS-663068 1200 mg Q12H + RTV 100 mg Q12H; Group 4 - BMS-663068 1200 mg Q12H + RTV 100 mg QAM; Group 5 - BMS-663068 1200 mg Q12H.

Each regimen group will consist of 10 subjects. Subjects in each regimen will be randomized and stratified by prior antiretroviral treatment history (ARV naive versus ARV experienced). ARV naive is defined as; no prior ARV therapy of ≥ 1 week. Each regimen group will contain approximately the same distribution of ARV naive and ARV experienced subjects. No more than 70% of the total population (or within each regimen group) will be ARV naive or ARV experienced. All regimen groups may initiate dosing simultaneously. Subjects will be confined to the clinical facility until Day 11. Subjects will return to the unit on Day 15 for a follow-up visit and on Day 50 for discharge procedures. Subjects may have a ± 3 day window around the discharge visit day (Day 50). Safety assessments consisting of ECGs, vital signs, physical exams and clinical laboratory tests will be conducted at screening and at selected time points throughout the study.

All doses will be administered under fed conditions. Subjects in Group 2 (QHS regimen group) will receive study drug every 24 hours in the evening (PM) from Day 1 to Day 8. Subjects in Group 4 (RTV QAM regimen group) will receive BMS-663068 every 12 hours and RTV every 24 hours in the morning (with BMS-663068) from Day 1 to Day 8. Subjects in Groups 1, 3 and 5 (Q12H regimen group) will receive study drug every 12 hours from Day 1 to Day 8.

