5.2 Method of Assigning Subjects to a Treatment

Subjects in each group will be randomized and stratified by prior antiretroviral (ARV) treatment history (ARV naive versus ARV experienced). No more than 70% of the total population will be ARV naive or ARV experienced. All regimen groups may initiate dosing simultaneously.

Subjects will be randomized to a group according to a computer-generated randomization scheme. The Randomization schedule will be prepared by a Randomization Coordinator within the Drug Supply Management Department of the Bristol-Myers Squibb Research and Development or the designated CRO.

All enrolled subjects will be assigned a sequential subject number starting with PPD at the time the study specific ICF is signed. Screen failures will keep their subject number assigned at enrollment. Enrolled subjects meeting inclusion and exclusion criteria will be randomized. Randomization numbers will be assigned prior to dosing for each group.

Subjects will not be replaced.

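### The combined-population Day 9 regimen t-tests omit the ARV-history stratum used in randomization; a stratum term would sharpen them if the strata differ, and would allow a direct naive-versus-experienced estimate

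*Protocol*

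**What the plan says.** Section 8.4.5 names the method for regimen comparisons of the Day 9 change in HIV RNA: "Two groups t-test will be used to test the differences in mean" log10 decrease "between two regimen groups by antiretroviral treatment history (ARV naive, ARV experienced, and combined [ARV naive + ARV experienced"]). The Statistical Analysis part of the synopsis says the same. No model with a stratum term is named for HIV RNA.

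Section 5.2 states: "Subjects in each group will be randomized and stratified by prior antiretroviral (ARV) treatment history". Section 4.1 adds a limit on the mix: "No more than 70% of the total population (or within each regimen group) will be ARV naive or ARV experienced". With 10 subjects per regimen, each stratum within a regimen therefore holds 3 to 7 subjects.

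Section 1.4 explains the stratification. In the earlier study, "antiviral effect of BMS-488043 was greater in treatment naive patients compared to treatment experienced patients". Viral susceptibility and drug exposure also "were lower in treatment experienced patients compared to treatment naive patients". So "the current study will be stratified to assess the antiviral activity of BMS-626529 in antiretroviral naive versus experienced subjects to reassess the prior finding". Section 2.3 carries this into an exploratory objective: "To explore the difference in antiviral activity of BMS-626529 following multiple regimens of BMS-663068 with and without RTV by prior antiretroviral (ARV) treatment history".

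Section 8.4.5 does report by ARV history. It gives changes with 90% confidence intervals on Days 2 to 11 and Day 15, regimen t-tests within each history group, and each subject's maximum decrease. None of these sets naive against experienced subjects directly.

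**The concern.** The trial stratifies on a factor that it has some reason to think prognostic, then leaves that factor out of the pooled comparison. Stratified allocation balances ARV history between regimens, so the true sampling error of a regimen difference shrinks. The two-group t-test cannot use this, because its error term still contains the spread between naive and experienced subjects. If the strata differ, the intervals are too wide and power is lost.

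The second part concerns the purpose of stratifying. A reader who wants to know whether the earlier naive-experienced finding recurs must compare two subgroups of 3 to 7 subjects by eye, one regimen at a time. The data from all 50 subjects could answer the averaged question much more precisely.

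**Working it through.** **Inputs.** From Section 8.1: 10 subjects per regimen, difference 0.6 log10, SD 0.5, stated power 82%. From Section 4.1: five regimens and a stratum mix between 30/70 and 70/30. Assumed:
- Two-sided 10% level. None is stated for the test; this matches the 90% intervals and returns the stated power.
- Naive-experienced gap g of 0, 0.3 or 0.5 log10, because the Protocol gives no size.
- The same stratum counts in each regimen.
- SD 0.5 is the total SD, the natural reading of Section 8.1.

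**Step 1: the plan's own figure.** SE = 0.5 × √(2/10) = 0.2236. Noncentrality = 0.6/0.2236 = 2.683. With 18 df and critical value 1.734, power is 82.5%. The stated 82% is reproduced.

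**Step 2: split the variance.** With naive share p, total variance = w² + p(1−p)g², where w is the within-stratum SD. For 5/5 strata, w = √(0.25 − 0.25g²) = 0.500, 0.477, 0.433 at the three gaps.

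**Step 3: the planned t-test.** With balanced strata the gap cancels from the regimen difference, so its true SE is w√(2/10) = 0.2236, 0.2133, 0.1936. The t-test estimates a variance with expectation w² + (10/9)p(1−p)g² = 0.2500, 0.2525, 0.2569. That implies an SE of about 0.2236, 0.2247, 0.2267. The excess is the lost precision. Size and power come from simulation (table).

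**Step 4: the same two regimens with a stratum term.** SE = w√(2/10), 17 df, critical value 1.740. Noncentrality = 2.683, 2.813, 3.098. Power = 82.4%, 85.4%, 90.8%.

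| Assumed gap (log10) | 0 | 0.3 | 0.5 |
|---|---|---|---|
| t-test, actual size at nominal 10% | 10% | 8.5% | about 6% |
| t-test, power for 0.6 | 82% | 83% | 85% |
| Stratum term, power for 0.6 | 82% | 85% | 91% |
| t-test, mean 90% half-width | 0.382 | 0.384 | 0.388 |
| Stratum term, mean 90% half-width | 0.383 | 0.366 | 0.332 |

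The interval is narrower by 1 − 0.366/0.384 = 5% and 1 − 0.332/0.388 = 14% at the two non-zero gaps. With 7/3 strata (w = 0.500, 0.481, 0.444), power is 82%, 83%, 85% for the t-test and 82%, 85%, 89% with the stratum. One model for all five regimens (44 df, 5/5 strata) gives 84%, 87%, 92%. The extra 1 to 2 points come from pooling variance over regimens, not from the stratum.

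**Step 5: naive minus experienced.** 90% half-width = t × s × √(1/n₁ + 1/n₂). At residual SD s = 0.5:
- One regimen (8 df, t = 1.860): 5 v 5 gives 1.860 × 0.5 × √(2/5) = 0.588; 7 v 3 gives 1.860 × 0.5 × √(1/7 + 1/3) = 0.642.
- All 50 (44 df, t = 1.680): 25 v 25 gives 1.680 × 0.5 × √(2/25) = 0.238; 35 v 15 gives 1.680 × 0.5 × √(1/35 + 1/15) = 0.259.

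The second line does not depend on additivity. The equally weighted average of the five within-regimen gaps (40 df, t = 1.684) gives 0.238 and 0.260.

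On the total-SD reading with a gap of 0.5, s is 0.433 (5/5) or 0.444 (7/3). The same formulas then give 0.509 and 0.570 in one regimen, and 0.206 and 0.230 on all 50.

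A difference in the gap between two regimens has half-width 0.5 × 1.684 × √(4/5) = 0.753 (5/5) to 0.5 × 1.684 × √(2 × (1/7 + 1/3)) = 0.822 (7/3), so it cannot be resolved.

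**The case against.** The strongest reply is that nothing here is an error. The t-test controls its size, Section 8.1 powers this same comparison, and the activity judgement rests on the mean decrease within a regimen. The gain depends on a gap seen with a different compound, which Section 1.4 itself calls unexpected and unexplained. A gap of 0.5 is large beside the declines of more than 0.7 log10 which that section reports for the compound. A contrast for an exploratory objective could also be left to an analysis plan.

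Most of this stands, and it is why the point is optional. It does not remove the point about the stratum term: the Protocol itself names the unadjusted test, so this is a method already fixed. Including a factor used in the randomization costs almost nothing. The missing contrast alone would be weak ground; it is raised because the same model supplies it.

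Three stronger readings might be inferred, and the Protocol supports none of them:
- **The t-test inflates false positives.** With balanced strata it errs the other way.
- **The 82% is overstated.** That needs 0.5 to be the within-stratum SD, in which case t-test power would be 80.4% at a gap of 0.3 and 76.2% at 0.5. Section 8.1 does not say so and describes the SD of the change without reference to strata.
- **ARV history is ignored.** Section 8.4.5 reports by history in several ways; only a direct contrast is absent.

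**Conclusion.** The point holds as an efficiency improvement, with optional weight. In the combined population the planned t-test is valid, but conservative if naive and experienced subjects respond differently. A stratum term adds about 2 points of power at an assumed gap of 0.3 log10 and about 6 at 0.5, and nothing at a gap of 0. These figures rest on total SD 0.5, a two-sided 10% level and equal stratum counts across regimens. The within-regimen 1 log10 criterion does not change.

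The larger gain is for the question behind the stratification: the averaged naive-minus-experienced difference is estimated about two and a half times as precisely on all 50 subjects as within one regimen (0.588/0.238 = 2.5). That ratio hardly depends on which SD is meant. Whether the gap varies by regimen stays out of reach at this sample size.

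**What to change.** In Section 8.4.5 and the synopsis, for the combined-population comparison only, replace the t-test with wording such as: *The Day 9 change from baseline in log10 HIV RNA will be analysed in a linear model with regimen group and ARV-history stratum. Regimen differences will be reported with 90% confidence intervals. As an exploratory analysis, the naive-minus-experienced difference, averaged over regimens, will be estimated with its 90% confidence interval from a model on all subjects.*

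The regimen comparison may be fitted to the two regimens concerned, or to all five if a common residual variance is accepted across regimens that differ in dose, frequency and boosting. Leave the within-stratum t-tests and the summaries by ARV history as planned.

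The cost is wording; no data or subjects are added, and Section 8.4.4 already uses general linear models for pharmacokinetics. If ARV history is not prognostic, the two-regimen model loses one degree of freedom, about 0.2 points of power (82.5% to 82.4% before rounding), and gains nothing from the stratum. The naive-minus-experienced estimate is an average if the gap varies by regimen, which is plausible given the lower exposure and susceptibility reported for experienced patients, and should be labelled so.

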1.3.1.2 BMS-626529

BMS-626529 is an attachment inhibitor that binds to the HIV-1 envelope glycoprotein gp120 and selectively inhibit the interaction between the virus and its host receptor CD4, thereby preventing the fusion of viral and cellular membranes.

In cell culture assays, BMS-626529 blocked the infection of eight of nine macrophage-, T-, and dual tropic laboratory strains of B subtype HIV-1 with EC₅₀ values ranging from 0.41 to 58 nM (the ninth strain had an EC₅₀ value of >2000 nM). It also exhibited potent antiviral activity against non-subtype B clinical isolates, with a median EC₅₀ of 2.8 nM. BMS-626529 was inactive against HIV-2 strain 287 and other RNA viruses. It did not affect the major HIV-1 enzymes, reverse transcriptase, protease, or integrase, and its activity was minimally affected (1.5 to 2.1 fold increase in EC₅₀) by the presence of 40% human serum. Cytotoxicity in cell culture was low, with EC₅₀ values ranging from 105 to > 200 µM in 13 cell lines examined. Finally, in a two-drug combination study in cell culture, BMS-626529 showed additive to synergistic interactions with 19 approved anti-HIV drugs. No antagonism of antiviral efficacy, or enhancement of cytotoxicity was seen with any of the two-drug combinations. Thus, BMS-626529 is a potent attachment inhibitor which merits further investigation for possible use in anti-HIV combination therapy.

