Plasma HIV RNA levels will be measured pre-AM drug administration on the mornings of Day 1 to Day 8 in groups 1, 3, 4 and 5 and Pre-PM drug administration in group 2. On days when dose is not administered, sample collection time should be maintained. Serial blood samples for pharmacokinetic determinations will be obtained on Days 1 and 8-11. Blood samples for trough concentrations will be obtained on Days 5 through 7 prior to morning study drug administrations (prior to evening administration for Group 2, QHS regimen group) for C_{trough} and steady-state assessment. In addition, blood samples for protein binding assay will be collected at specified timepoints throughout the study and selected regimen groups will be analyzed.

Blood for CD4⁺ and CD8⁺ lymphocyte counts and percents and activated (DR⁺) CD4⁺ and CD8⁺ subsets, genotyping, phenotyping, HIV co-receptor usage (CCR5 versus CXCR4), exploratory resistance analysis, measurement of neutralizing antibody activity will be collected at specified timepoints throughout the study. These samples may be analyzed if deemed relevant. Screening samples for population RT/Pol genotyping to confirm that all subjects are infected with clade B HIV will be analyzed in all enrolled subjects. Day 1 predose samples for envelope phenotyping will be collected and analyzed for all randomized subjects.

Approximately 800 mL of blood will be drawn from each subject during the study.

The approximate duration of the study is 88 days. Study participation includes a 35-day screening period, 8-day treatment and 2 follow-up visits.

End of the study will be the date of the last visit of the last subject undergoing the study. Last visit will be the last follow-up visit of a subject.

At the end of the study, the sponsor will not continue to supply study drug to subjects/investigators unless the sponsor chooses to extend the study. The investigator should ensure that the subject receives appropriate standard of care to treat the condition under study.

Table 4.1 summarizes the study design and study parameters.

Table 4.1: AI438006 Study Design

	Regimen Group 1 (N=10)	Regimen Group 2 (N=10)	Regimen Group 3 (N=10)	Regimen Group 4 (N=10)	Regimen Group 5 (N=10)
Dose and Regimen	600 mg BMS- 663068 Q12H + 100 mg RTV Q12H	1200 mg BMS- 663068 QHS + 100 mg RTV QHS	1200 mg BMS- 663068 Q12H + 100 mg RTV Q12H	1200 mg BMS- 663068 Q12H + 100 mg RTV QAM	1200 mg BMS- 663068 Q12H
Days subjects receive BMS-663068	Day 1-8				

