6.6 Pharmacodynamics Assessments

Viral activity will be assessed by the magnitude and rate of change in plasma HIV RNA levels from baseline (predose Day 1). Blood samples from all subjects will be obtained for analyses of HIV RNA level at Screening, on Days 1 through 11, 15 and discharge. Samples should be collected prior to dosing (pre AM dose in groups 1, 3, 4, and 5; pre PM dose in group 2). The plasma collection time (relative to dosing) should be maintained throughout the inpatient portion of the study (Days 1 through 11).

CD4+ and CD8+ lymphocyte counts and percents will be assessed. Blood samples from all subjects will be obtained for CD4+ and CD8+ cell counts at Screening, Days 1, 8, 15

and discharge. Samples should be collected prior to dosing (pre AM dose in groups 1, 3, 4, and 5; pre PM dose in group 2). Collection time (relative to dosing) should be maintained throughout the inpatient portion of the study (Days 1 through 11).

RT/Pol genotyping to determine HIV clade will be performed. A plasma sample will be obtained at screening for RT/Pol genotype and HIV clade determination.

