8 STATISTICAL CONSIDERATIONS

8.1 Sample Size Determination

The sample size evaluation is based on the primary objective of the study, to assess the antiviral activity of BMS-626529 following administration of selected regimens of BMS-663068 with and without RTV administered orally to HIV infected subjects for 8 days. A mean decrease from baseline in HIV RNA of at least 1 log₁₀ at Day 9 within any one regimen group may suggest that the dose of BMS-663068 is sufficiently active against HIV to proceed with further development of the drug. If the BMS-663068 containing regimen has no effect, then administration of the regimen to 10 subjects (ARV naive or experienced) would provide a ≤1% probability to observe a mean log₁₀ drop of ≥1. If the true population mean decrease from baseline in HIV RNA is ≥1.5 log₁₀, then there would be a 99% probability that the observed mean decline from baseline would be ≥1 log₁₀. In addition, 10 subjects within each group can also provide >99% power to conclude the mean decreases in log₁₀ HIV RNA from baseline > 0 if the true population decrease from that group is 1 log₁₀. Meanwhile, 10 subjects in each group can also provide 82% power to conclude the mean decreases in log₁₀ HIV RNA from two groups are different if the true difference in population mean decreases from these two groups is 0.6 log₁₀.

In addition, administration of the BMS-663068 containing regimen to 10 subjects per group provides an 80% probability of observing at least one occurrence in that regimen group of any adverse event that would occur with 15% incidence in the population from which the sample is drawn.

For these calculations, it is assumed that the \log_{10} decrease in HIV RNA from baseline to Day 9 is normally distributed, with a standard deviation of 0.5, as estimated from AI430003.

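### Day 9 regimen comparisons use separate unadjusted two-group t-tests; one five-group model with baseline HIV RNA would cost essentially nothing and may be more precise

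*Protocol*

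**What the plan says.** Section 8.4.5 fixes the endpoint: "The primary assessment of the antiviral activity of BMS-663068 will be based on the log₁₀ change from baseline in HIV RNA to Day 9". For comparisons between regimens it says that "Two groups t-test will be used to test the differences in mean" log10 decrease at Day 9, in ARV-naive, ARV-experienced and combined subjects. The synopsis says the same. No covariate is named, so baseline HIV RNA enters only as the value subtracted.

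Section 8.1 claims that "10 subjects in each group can also provide 82% power" when the "true difference in population mean decreases from these two groups is 0.6" log10, "with a standard deviation of 0.5, as estimated from AI430003".

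Both baseline measurements are collected. Section 6.6 takes HIV RNA predose on Day 1 as baseline in all subjects. Section 4.1 says: "Day 1 predose samples for envelope phenotyping will be collected and analyzed for all randomized subjects". Randomization is stratified by ARV history only. Section 8.4.5.1 uses EC90 descriptively: a scatter plot against response, then by-group summaries that leave out subjects above a threshold read from that plot.

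**The concern.** With 10 subjects per group, two features of the named test look wasteful. Each comparison estimates its variance from 20 of the 50 subjects. A change score also leaves in any variance that is related to the baseline value.

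Susceptibility raises a separate question of interpretation. Section 1.4 reports that in the earlier attachment-inhibitor study the group with the smaller antiviral effect also had lower viral susceptibility and lower drug exposure. Section 1.3.1.2 reports that eight of nine subtype B laboratory strains were inhibited, while "the ninth strain had an EC₅₀ value of >2000 nM". If one regimen happens to receive more subjects with poorly susceptible virus, its mean decline will be smaller, and the planned test offers no adjusted contrast to set beside that result. The data feed internal decisions that may include phase IIb dose selection (section 8.5).

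**Working it through.** **Inputs from the protocol:** five groups of 10; SD of change 0.5; difference 0.6 log10. The level of the test is not stated. The 90% confidence intervals in section 8.4.5 suggest two-sided 10%.

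**Step 1: the plan's own figure.** The standard error is 0.5 × √(1/10 + 1/10) = 0.2236, and the noncentrality is 0.6 / 0.2236 = 2.68 with 18 df. Power is 82.5% at two-sided 10% and 71.8% at two-sided 5%. The stated 82% is therefore reproduced at 10%. The 90% interval has width 2 × 1.734 × 0.2236 = 0.775 log10.

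**Step 2: pool the variance over five groups, no covariate.** The df become 50 − 5 = 45. Power is 84%, and the width is 2 × 1.679 × 0.2236 = 0.751, about 3% narrower.

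**Step 3: add baseline log10 HIV RNA.** Let s0 and s9 be the baseline and Day 9 SDs; the protocol gives neither. Since s9² = s0² + 0.25 + 2 × cov(baseline, change), the covariance is (s9² − s0² − 0.25)/2. The share of change-score variance explained by baseline is then R² = cov² / (s0² × 0.25) = (s9² − s0² − 0.25)² / s0². The standard error of a difference is about 0.5 × √(1 − R²) × √(0.2 × (1 + 1/43)), with 44 df. The factor 1 + 1/43 is the average cost of estimating the slope.

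| Assumed s0 / s9 | R² | SE | Power | 90% CI width |
|---|---|---|---|---|
| 0.5 / 0.5 | 0.25 | 0.196 | 91% | 0.66 |
| 0.6 / 0.6 | 0.17 | 0.206 | 89% | 0.69 |
| 0.7 / 0.7 | 0.13 | 0.211 | 88% | 0.71 |
| 0.6 / 0.7 | 0.04 | 0.222 | 85% | 0.74 |
| 0.6 / 0.78 | about 0 | 0.226 | 83% | 0.76 |
| 0.5 / 0.707 | about 0 | 0.226 | 83% | 0.76 |

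Simulation agrees and spans about 82 to 92%. The gain is real when the two SDs are equal. It disappears as the Day 9 variance approaches the baseline variance plus 0.25. Even then, the five-group model is level with the t-test.

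**Step 4: error rate.** In simulation with no true difference, the t-test and a two-group covariate-adjusted comparison both rejected in about 10% of runs at the 10% level.

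**Step 5: susceptibility, as an illustration only.** Assume that 1 in 9 subjects carries virus that does not respond and that the others fall by 1.5 log10. The counts in two groups of 10 are then independent Binomial(10, 1/9), and they differ by two or more with probability 27%. At other assumed prevalences the probability is 11% (5%), 24% (10%) and 39% (20%). A difference of two subjects moves the contrast by (2/10) × 1.5 = 0.30 log10, half of the 0.6 design difference. If the lost response is 1.0 log10, the shift is 0.20.

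**The case against.** The strongest reply is that nothing here is wrong: under randomization the t-test keeps its error rate, and its power claim is correct for the stated inputs. That stands. Four stronger readings are tempting, and the documents do not support them.

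- **A reader might infer that chance imbalance biases the test or inflates false positives.** It does not (Step 4). Imbalance is ordinary sampling error that the test already allows for. It matters only for interpreting one particular result.
- **A reader might infer that precision is certainly lost.** That depends on an R² the protocol does not give. An adjusted model fitted to two groups at a time, with two covariates, would lose power if they explained little: 78% at R² = 0 and 82% at R² = 0.1, against 82.5% for the t-test. The five-group model avoids that loss.
- **A reader might infer from the non-responder scenario that true power is about 57 to 66%.** Those simulated figures add a between-subject variance of (1/9)(8/9)(1.5²) = 0.22 to the planned 0.25, giving an SD of about 0.69. The planned 0.5 comes from an attachment-inhibitor study in infected subjects, so it may already contain variation in susceptibility. The 1-in-9 figure comes from laboratory strains, not patients.
- **A reader might infer that EC90 is ignored.** Section 8.4.5.1 examines it, and inhibitory quotients are analyzed too. What is missing is an adjusted regimen contrast.

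Two further objections also stand. The development criterion is a within-group mean fall of at least 1 log10, so the pairwise tests are subsidiary. EC90 also makes a poor main-model covariate: the protocol anticipates a threshold relation, values may lie above the assay limit, and subjects without a phenotype would drop out of groups of 10.

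**Conclusion.** The point holds as an efficiency improvement. The protocol names a valid but unadjusted test that leaves three of the five groups out of each variance estimate and makes no covariate use of a baseline value measured in everyone. Against 82.5% for the planned test, the five-group model with baseline HIV RNA has about 82 to 92% power, and the 90% interval goes from 0.775 to about 0.66–0.76 log10. These figures assume a two-sided 10% level, a common SD of change of 0.5 in all groups, and the baseline and Day 9 SDs shown. Only the lower end of the gain, essentially none, can be relied on without knowing those SDs. The 1-in-9 prevalence and the 0.30 log10 shift are illustrative assumptions. They justify a supportive look at susceptibility, not a claim that the planned comparison is misleading.

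**What to change.** In section 8.4.5 and the synopsis, replace the combined-population two-group t-tests by one linear model of Day 9 log10 change on regimen (five levels) and baseline log10 HIV RNA. Report pairwise differences with 90% confidence intervals from the pooled residual variance, and state the significance level.

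Prespecify one supportive model that adds log10 Day 1 protein-binding-adjusted EC90, fitted in subjects with a phenotype and with a stated rule for values above the assay limit. Its purpose is to show whether an observed regimen difference persists once susceptibility is accounted for. Keep the unadjusted group means for the 1 log10 criterion.

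The cost is a change of wording and a few lines of code; no new samples are needed. The main model spends one degree of freedom on baseline and gains 27 by pooling (45 against 18). It assumes a common residual variance and a common baseline slope across the five regimens, which should be checked. The supportive model loses any subject without a phenotype, which is why it should not be the main comparison.
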